## 7.5 Definition of Maximum Tolerated Dose (MTD)

The MTD will be defined as the highest dose at which 20% of the patients experienced a DLT. The first cohort of patients (3 patients) will be started at dose level 1, and each patient will be observed for 4 weeks on the specified dose. No new cohort of patients will be treated until the previous cohort has been fully evaluated for toxicity and a dose escalation decision has been made. Routine updates regarding patient and study status will be conducted.

Once the MTD is reached, the safety data will be analyzed and the expansion component of the study will be completed to assess tolerability and efficacy. Patients in the phase II portion of the study will initiate study treatment at the MTD defined in the escalation component of the trial. Note that dose reduction within patients (individually) is allowed after the 4 week DLT observation period in the escalation and in the expansion components of the study (see Dose Modification guidelines, Section 8). Intrapatient dose escalation will not be allowed. Dose reduction will be required for a given patient in case of:

- Grade 3 or 4 toxicities
- Grade  $\geq 2$  hyperphosphatemia lasting more than 21 days despite medical treatment, or
- Grade  $\geq 2$  ocular toxicity lasting more than 28 days despite medical treatment, or
- Grade  $\geq 2$  elevation of creatinine, bilirubin, AST, or ALT lasting more than 14 days despite medical treatment, or
- Grade  $\geq 2$  skin or nail toxicity for more than 28 days in a row despite optimal medical treatment, or

- Grade  $\geq$  2 GI toxicity lasting more than 14 days despite medical treatment.

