Grade 2	
Immediately omit erdafitinib and refer to ophthalmologic exam.
 
If keratitis or retinal abnormality are detected, omit erdafitinib until signs and symptoms have resolved; follow specific treatment as per ophthalmologist's recommendations.
 
For retinal pathology perform OTC as appropriate and consider referral to a retina specialist for further evaluation.
 
Monitor for recurrence every 1-2 weeks for a month and as clinically appropriate thereafter.
 
If toxicity is reversible (complete resolution or stabilization and asymptomatic) in 4 weeks according to ophthalmologist exam, resume erdafitinib at the next lower dose level if patient is deriving clinical benefit from treatment, after consultation with Protocol Chair.

Grade 3	
Immediately discontinue erdafitinib, refer to ophthalmologic exam, report as SAE.
 
If keratitis or retinal abnormality are detected, omit Erdafitinib until signs and symptoms have resolved; follow specific treatment as per ophthalmologist's recommendations.
 
For retinal pathology perform OTC as appropriate and consider referral to a retina specialist for further evaluation.
 
If toxicity is reversible (complete resolution or stabilization and asymptomatic) in 4 weeks according to ophthalmologist exam, resume erdafitinib at 2 lower dose levels if patient is deriving clinical benefit from treatment, after consultation with Protocol Chair.
 
Continue to monitor for recurrence of toxicity every 1-2 weeks for a month and as clinically appropriate thereafter, using appropriate investigations. For cases of recurrence, permanently discontinue erdafitinib.

Grade 4	
Immediately discontinue erdafitinib permanently, refer to ophthalmologic exam, report as SAE.
 
Continue to monitor for recurrence of toxicity every 1-2 weeks for a month and as clinically appropriate thereafter, using appropriate investigations.

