## GI disorders

### Constipation (for erdafitinib only)

Grade 1	Maintain dose level of erdafitinib, but initiate anti-constipation treatment.
Grade 2	Omit dose of erdafitinib until resolved to CTCAE Grade ≤ 1, then maintain dose level of erdafitinib.

Grade 3	Omit dose of erdafitinib until resolved to CTCAE Grade ≤ 1, then reduce dose of erdafitinib by 1 dose level.
Grade 4	Discontinue erdafitinib.
Diarrhea (for palbociclib only)	
Grade 1	Maintain dose level of palbociclib, initiate anti-diarrhea treatment per standard practice.
Grade 2	Initiate anti-diarrhea treatment per standard practice.  Omit dose of palbociclib until resolved to CTCAE Grade ≤ 1, then maintain dose level of palbociclib.  For 2nd occurrence of diarrhea CTCAE Grade 2, omit dose of palbociclib until resolved to CTCAE Grade ≤ 1, then reduce palbociclib by 1 dose level.
Grade 3	Initiate anti-diarrhea treatment per standard practice.  Omit dose of palbociclib until resolved to CTCAE Grade ≤ 1, then reduce dose of palbociclib by 1 dose level.  For 2nd occurrence of diarrhea CTCAE Grade 3, discontinue palbociclib.
Grade 4	Initiate anti-diarrhea treatment per standard practice.  Discontinue palbociclib.
Note: Antidiarrheal medication per standard practice is recommended at the first sign of abdominal cramping, loose stools or overt diarrhea.	
Mucositis	
Grade 1	Continue palbociclib and erdafitinib at same doses.  Topical steroid moderate strength and lidocaine 2-5% jelly or solution QID.
Grade 2	Continue palbociclib and erdafitinib at current dose.  Dexamethasone solution (3.3 mg/5 mL) swish and spit QID and lidocaine 2-5% jelly or solution QID.  Consider study drug holding if no improvement in 1 week.  When resolves to ≤Grade 1 or baseline, restart at same or 1 dose level below in consultation with the medical monitor.
Grade 3	Hold palbociclib and erdafitinib (for up to 28 days), with weekly reassessments of clinical condition.  Dexamethasone solution (3.3 mg/5 mL) swish and spit QID and lidocaine 2-5% jelly or solution QID  When resolves to ≤Grade 1 or baseline, restart at 1 dose level below in consultation with the medical monitor.
Grade 4	Discontinue palbociclib and erdafitinib; evaluation and therapy as clinically indicated.
Skin and subcutaneous disorders (for erdafitinib only)	
Skin toxicity	

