Grade 1	Maintain dose level of erdafitinib.  Use fragrance free moisturizing cream or ointment BID over entire body.  Use ammonium lactate 12% cream or salicylic acid 6% cream BID over dry/scaly/hyperkeratotic areas such as palms and soles.

Grade 2	Maintain dose level of erdafitinib.  Use fragrance free moisturizing cream or ointment BID over entire body.  Use ammonium lactate 12% cream or salicylic acid 6% cream BID over dry/scaly/hyperkeratotic areas such as palms and soles.  Use zinc oxide 13-40% at night for areas with fissures.
Grade 3	Omit erdafitinib doses for up to 28 days, with weekly assessments of clinical condition.  Use topical steroid ointment or cream (Clobetasol 0.05%, Betamethasone 0.05%, Fluocinonide 0.05%) BID and zinc oxide 13-40% at night for areas with fissures.  Once resolved to grade ≤ 1 then:  - If resolved in ≤ 14 days, ↓ 1 dose level of erdafitinib. - If resolved in > 14 days, discontinue patient from erdafitinib.
Grade 4	Discontinue erdafitinib; therapy as clinically indicated.
Nail toxicity	
Grade 1	Maintain dose level of erdafitinib.  Over the counter nail strengthener OR poly-urea urethane nail lacquer (Nuvail) OR diethylene glycol monoethylether nail lacquer daily (Genadur).
Grade 2	Maintain dose level of erdafitinib.  For signs of infection (periungal edema/erythema/ tenderness and/or discharge), start the following:  - treatment with oral antibiotic for 2 weeks (cefadroxil 500 mg BID, ciprofloxacin 500 mg BID, or sulfamethoxazole/ trimethoprim (Bactrim®) DS BID) AND  - topical antifungal lacquer daily for 6+ weeks (ciclopirox olamine 8% OR efinaconazole 10% OR amorolfine 5% weekly OR bifonazole/urea ointment daily)  Consider study drug holding if no improvement in 1 to 2 weeks.  When resolved to ≤ Grade 1 or baseline, restart at same or 1 dose level below in consultation with the medical monitor.

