
 
• All dose modifications should be based on the worst preceding toxicity. Once a dose has been reduced it will not be increased at a later time even if there is no toxicity. Patients who require dose reductions of palbociclib and erdafitinib past the lowest dose level will be discontinued from study drugs treatment.
 
• If a patient requires a dose delay of <math>> 28</math> consecutive days from the intended day of the next scheduled dose of palbociclib and erdafitinib, due to study related interventions, then the patient must be discontinued from the study treatment. Patients that require a dose delay of <math>> 28</math> days due to a cause unrelated to study participation will have the opportunity to continue study if deemed eligible to do so by the Protocol Chair of the study. Patients who discontinue from the study for a study-related AE or an abnormal laboratory value must be followed at least once a week for 4 weeks and subsequently at 4-week intervals, until resolution or stabilization of the event, whichever comes first, except specifically mentioned.
 
	

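### Sections 7.5 and 8.4 give conflicting mandatory erdafitinib instructions for prolonged Grade 2 skin toxicity and constipation, and with a third list in 17.2.1 the 15-of-20 tolerability rule has no single referent

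*Combined protocol and SAP*

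**What the plan says.** **Section 7.5** ends with a list introduced by "Dose reduction will be required for a given patient in case of". For toxicity of Grade 2 or worse, the entries include "ocular toxicity lasting more than 28 days despite medical treatment", "skin or nail toxicity for more than 28 days in a row despite optimal medical treatment" and "GI toxicity lasting more than 14 days despite medical treatment". Hyperphosphatemia has a 21-day limit. The list does not name the drug to be reduced. Section 8 is cited only where 7.5 says that reductions within a patient are allowed after the DLT window.

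**Section 8.4, Grade 2 rows:**
- Skin (erdafitinib only): "Maintain dose level of erdafitinib", plus topical care. There is no time limit and no hold.
- Constipation (erdafitinib only): hold until Grade 1 or less, "then maintain dose level of erdafitinib". Duration plays no part.
- Eye (erdafitinib only): hold at once and refer for examination. If the event is reversible in 4 weeks, "resume erdafitinib at the next lower dose level if patient is deriving clinical benefit from treatment", after consulting the Protocol Chair. The row is silent on resumption after 4 weeks.
- The closing note covers a delay of palbociclib and erdafitinib of more than 28 consecutive days for study-related reasons: "then the patient must be discontinued from the study treatment".

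**Section 17.2.1** has its own list of required reductions: Grade 3 or 4 toxicity, or Grade 2 creatinine, bilirubin, AST, ALT, hyperphosphatemia or GI toxicity beyond 2 weeks. The same section bases the recommended phase II dose on at least 15 of 20 patients tolerating a given dose level for 8 consecutive weeks without toxicities that it identifies only as those cited before.

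**The concern.** A protocol may set different triggers for different purposes. Here, however, two sections each tell the site what to do with the same drug in the same patient, and the instructions cannot both be followed. A site that applies the 8.4 skin row literally breaches 7.5 once the event has lasted more than 28 days.

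Two quantities depend on which text is used:

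1. **Dose received.** A reduction is largely one-way. Section 7.5 bars intrapatient escalation, and the closing note of 8.4 says a reduced dose will not later be raised.
2. **Tolerability classification.** The rule turns on staying at a dose level and on not developing the toxicities cited before. If that phrase points to 7.5, a 29-day Grade 2 skin event counts against tolerance. If it points to the list in 17.2.1, the event does not. The tolerability population is patients with at least 8 weeks of erdafitinib, so a permanent stop can also change the denominator.

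**Working it through.** **Step 1. The rules side by side (Grade 2)**

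| Event | 7.5 | 8.4 | 17.2.1 list | Relation of 7.5 to 8.4 |
|---|---|---|---|---|
| Skin, >28 days | Reduction required | Same dose, no limit | Not listed | Direct conflict |
| Constipation, >14 days | Reduction required (as GI) | Hold, then same dose | GI >2 weeks: reduction | Direct conflict |
| Eye with keratitis or retinal abnormality, up to 28 days | No mandatory trigger | Hold; one level lower if reversible in 4 weeks and benefiting | Not listed | Misaligned; following 8.4 breaches nothing in 7.5 |
| Same, >28 days | Reduction required | No resumption path stated | Not listed | Misaligned; 8.4 silent |
| Nail, >28 days | Reduction required | Same dose; optional hold; restart at same or one lower level | Not listed | Weaker: 8.4 permits a lower dose |
| Mucositis, >14 days, if counted as GI | Reduction required | Continue; optional hold; restart at same or one lower level | GI >2 weeks: reduction | Weaker, same reason |

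The diarrhea rows of 8.4 concern palbociclib only, so they raise no erdafitinib conflict. Hyperphosphatemia shows that 7.5 and 17.2.1 also differ from each other: 21 days against 2 weeks.

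**Step 2. Is there a precedence rule?** Section 8.3.2 bases the need for reduction at resumption on the table. That leans towards 8.4 for constipation, where dosing is held and resumed, but it does not mention 7.5. It cannot settle Grade 2 skin toxicity, where 8.4 never interrupts dosing. Section 8.5 lets the investigator reduce for any grade or duration, which is permission and not precedence.

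**Step 3. Can the conflict fall inside the 8-week window?** Eight weeks is 56 days. A more-than-28-day trigger is first met on duration day 29, so onset by day 56 − 28 = 28 is early enough. A more-than-14-day trigger is first met on duration day 15, so onset by day 56 − 14 = 42 is early enough. Both can occur within the window.

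**Step 4. The plan's own figure.** With X ~ Binomial(20, p), P(X ≥ 15) at p = 0.3, 0.5, 0.7, 0.75, 0.8, 0.9 and 0.99 is 0.00004, 0.021, 0.416, 0.617, 0.804, 0.989 and 1.000. All agree with the row in 17.2.1. The arithmetic is right; the definition of a tolerant patient is what is unsettled.

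**Step 5. Sensitivity (assumed shares).** Suppose the choice of list moves a share q of patients from tolerant to non-tolerant. Then the probability is P(X ≥ 15) at p − q:

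| Base p | q = 0 | 0.05 | 0.10 | 0.15 | 0.20 |
|---|---|---|---|---|---|
| 0.80 | 0.804 | 0.617 | 0.416 | 0.245 | 0.126 |
| 0.90 | 0.989 | 0.933 | 0.804 | 0.617 | 0.416 |

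The documents give no value for q. The table shows how steep the rule is, not what will happen.

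**The case against.** The best defence is that 7.5 states when reduction becomes mandatory and does not forbid earlier action, so the two sections can be read as layers. Section 8.3.2 points to the table at resumption, 8.5 gives discretion and sends any change to the guidelines to the Protocol Chair, eye resumption already needs the Chair, and regular teleconferences across sites would surface differences.

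Much of this stands for eye events. A reader might infer that 7.5 and 8.4 disagree at every duration of a Grade 2 eye event, with a reduction under 7.5 and a stop under 8.4 beyond 28 days. The documents do not support that. Up to 28 days, acting under 8.4 violates nothing in 7.5. Beyond 4 weeks the eye row is silent. The 28-day delay rule speaks of palbociclib and erdafitinib together, whereas the eye row holds erdafitinib alone, and 8.5 lets patients continue fulvestrant and palbociclib if erdafitinib stops. The row also counts stabilization without symptoms as reversible, so event duration and hold duration can differ. Dry eye has its own guidance in 8.1.3.4.3 and 8.1.3.4.4, which need not conflict with 7.5.

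A reader might also turn the pooled rates in section 8.1.3 (eye 41.1%, nail 44.3%, skin 42.3%) into a count. Assuming 10–20% of 26–35 patients have a Grade 2 eye event gives 0.10 × 26 = 2.6 to 0.20 × 35 = 7. That is not a count of conflicted patients: the 10–20% is not in the documents, it includes events with no contradiction, and the pooled rates are not limited by grade or duration. Nor are these shown to be the commonest toxicities: 8.1.3.2 gives that place to hyperphosphatemia among events of clinical importance.

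The defence does not remove the skin conflict, and it only partly answers constipation. The layered reading is possible, but no text adopts it. That sites would in fact diverge is not shown.

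**Conclusion.** The inconsistency is established for Grade 2 skin toxicity beyond 28 days and, less strongly because of 8.3.2, for Grade 2 constipation beyond 14 days. This takes the reduction in 7.5 to mean erdafitinib, which the erdafitinib-only rows in 8.4 make the natural reading. Eye events with keratitis or a retinal abnormality are a misalignment that needs wording. Nail toxicity and mucositis are weaker cases.

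The third list in 17.2.1 is separate from 7.5 and leaves the 15-of-20 rule without a single definition of non-tolerance. The effect on that rule cannot be quantified from the documents. The most that can be said is that the triggers can fall inside the 8-week window and that the rule is sensitive: at a true tolerability of 0.80, an assumed shift of 5 percentage points lowers the probability of meeting it from 0.804 to 0.617.

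**What to change.** Reconcile 7.5, the Grade 2 eye, constipation, mucositis, skin and nail rows and closing note of 8.4, and the list in 17.2.1, so that one set of dose-reduction triggers governs and names the drug concerned. State which section takes precedence if any overlap remains, and say what happens to erdafitinib when a Grade 2 eye event is not reversible in 4 weeks.

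In 17.2.1, replace the backward reference in the recommended-dose rule with an explicit list, or a section number, that defines non-tolerance. The existing 17.2.1 list should not be deleted without that replacement, since it may be what the rule refers to.

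Which clinical rule applies is for the sponsor to decide. The cost is wording in 7.5, 8.4 and 17.2.1 in one amendment; the sample size and the 15-of-20 threshold do not change.

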## 7.6 Concomitant Treatment and Supportive Care Guidelines

Because there is a potential for interaction of erdafitinib and palbociclib with other concomitantly administered drugs through the cytochrome P450 system, the case report form must capture the concurrent use of all other drugs, over-the-counter medications, or alternative therapies. The Protocol Chair should be alerted if the patient is taking any agent known to affect or with the potential to affect selected P450 isoenzymes (Cautionary Concomitant Medications list). Patients taking any of the medications on the Cautionary Concomitant Medications list are encouraged to seek alternative medications; if not possible, patient will not necessarily be excluded from entering the study, but approval by the Study Chair has to be obtained prior to enrollment. Patients already enrolled in the study that initiate and persist taking any of the medications on the Cautionary Concomitant Medications list will also require approval from the Study Chair.

Patients on chronic medications that can be given concomitantly with erdafitinib and palbociclib should be maintained on the same dose and dose schedule throughout the study period, as medically feasible. The investigator should instruct the patient to notify the study site about any new medications he/she takes after the start of the study drug. All medications (other than study drug) and significant non-drug therapies (including physical therapy and blood transfusions) administered after the patient starts treatment with study drug, and any changes in dosing should be recorded.

All supportive measures consistent with optimal patient care can be given throughout the study at the discretion of the treating physician, as long as they are not part of the list of prohibited medications. In general, the use of any concomitant medication/therapies deemed necessary for the care of the patient is permitted with the following considerations:

- Prophylactic anti-emetics should be started only once the patient experienced nausea or vomiting at the discretion of the investigator.
- There are no concurrent supportive or prophylactic growth factor support regimens recommended for palbociclib. While the rates of grade III/IV neutropenia are considerable with CDK4/6 inhibitors, the rates of febrile neutropenia (FN) are quite low, and well below the 20% threshold for which FN prophylaxis with G-CSF is recommended. Nonetheless, G-CSF support will be allowed at the treating physician's discretion. Hematopoietic growth factors may be used according to ASCO guidelines
- Bone directed therapy to prevent skeletal related events (SRE's) or to treat osteoporosis with bisphosphonates or denosumab is permitted. While the use of bisphosphonates has been found to reduce the incidence of new bone metastases in patients with metastatic breast cancer, we do not anticipate this to affect the results of this trial. Thus, treatment initiated prior to registration or after registration with these agents is permitted. The time of initiation of bone directed therapy should be clearly recorded on the case report forms
- Local radiotherapy required for life-threatening situations (e.g., superior vena cava syndrome, spinal cord compression, central nervous system metastases) will require the patient to discontinue protocol treatment due to symptomatic deterioration. However, limited palliative radiotherapy (i.e., to bone metastasis) in subjects who are otherwise benefiting from study treatment will be allowed during the study but must be discussed with the Protocol Chair. Study treatment should be withheld until palliative radiotherapy is terminated. This treatment break should not be considered as treatment interruption. Palliative radiation is permitted if done solely for bone pain relief. It should not be delivered to a target lesion and it should not encompass more than 25% of irradiated bone marrow. If palliative radiotherapy is initiated

after the start of study treatment, the reason for its use must be clearly documented and progression as per RECIST 1.1 must be ruled out

- Other investigational therapies must not be used while the patient is on the study
- Anticancer systemic therapy other than the study treatments must not be given to patients while on the study. If such agents are required for a patient then the patient must be discontinued from the study
- Medications known to increase serum levels of phosphate, such as potassium phosphate supplements (oral or IV), vitamin D supplements, antacids, and phosphate-containing enemas and laxatives (oral/rectal) thought to increase serum phosphate levels. Medications known to have phosphate as an excipient should be avoided unless no alternatives exist
- Herbal preparations are not allowed throughout the study. These herbal preparations include, but are not limited to: St. John's wort, Kava, ephedra (ma huang), gingko biloba, dehydroepiandrosterone (DHEA), yohimbe, saw palmetto, and ginseng. Patients should stop using these herbal preparations 14 days prior to first dose of study drug

## 7.7 Duration of Therapy

Duration of therapy will depend on individual response, evidence of disease progression and tolerance. In the absence of treatment delays due to adverse events, treatment may continue until one of criteria in Section 7.9 applies.

## 7.8 Duration of Follow-Up

Participants will have a follow up at 28 days ( $\pm$  7days) after discontinuation of study drugs for any reason (unacceptable adverse events or disease progression) for toxicity assessments.

- Participants removed from study for unacceptable adverse events will be followed weekly until resolution or stabilization of a serious adverse event, and will be followed every three months (chart review) until disease progression, or until death from any cause (whichever occurs first) Patients continuing fulvestrant who have discontinued erdafitinib or palbociclib for any reason other than disease progression will be followed until disease progression as stated above

